9.2 Efficacy Analysis

All efficacy analyses will be provided for the Safety Population and will be repeated for the Efficacy Evaluable Population.

Rates will be calculated for each response category (sCR, CR, VGPR, PR, MR, SD, PD, missing) by visit (for C3D1, C6D1, and C12D1). Moreover, the ORR (PR or better), the CBR (MR or better) and the DCR (SD or better) will be calculated by visit (see section 7.3.3.1). The corresponding number of subjects in each of these response categories and all rates will be summarized in a frequency table by visit.

For best overall response, frequencies will be calculated for each response category (sCR, CR, VGPR, PR, MR, SD, PD, NE). Moreover, the ORR (PR or better), CBR (MR or better) and the DCR (SD or better) will be calculated, based on BOR per subject (see section 7.3.3.2). The corresponding number of subjects in each of these response categories and all rates will be summarized in a frequency table. The exact Clopper-Pearson 95%-confidence intervals for ORR, CBR and DCR will also be shown in combined presentations.

The denominator for calculating the rates (rates by visit and best response rates) will be the total number of subjects within the corresponding analysis group. In the summary of rates by visit, all withdrawals and protocol non-compliances after start of new anti-MM therapy will be analyzed as missing for all visits after withdrawal, and the counts of missing observations will be included into the denominator.

Both TTP and PFS will be analyzed using Kaplan-Meier methods. Kaplan-Meier tables for PFS and TTP will contain number of subjects, number of subjects with an event (non-censored subjects), percentage of subjects with an event, median time [months], 25% and 75% quantile. The 95%-confidence intervals for median, 25% quantile and 75% quantile will be provided in combined presentations.

Moreover, the percentage of subjects having an event after 2, 4 and 6 months together with the corresponding 95%-confidence intervals will be retrieved from the Kaplan-Meier curve in combined presentations.

For PFS, the reason for censoring as stated in Table 3 will be tabulated together with reasons for discontinuation (based on study completion page) for patients who discontinued the study without a PFS event. This information will be included in the listings as well together with detailed information concerning AE term(s) leading to withdrawal.

In these Kaplan-Meier analyses, the confidence intervals for the median will be calculated according to Brookmeyer and Crowley (1982) [12] and confidence intervals for the quartiles according to Klein and Moeschberger (1997) [13] who generalized the methods developed by Brookmeyer and Crowley. Confidence intervals for the survival function estimates at above

defined time points will be derived using the log-log transformation according to Kalbfleisch and Prentice (1980) [14] ([REDACTED]). The estimate of the standard error will be computed using Greenwood's formula.

Time to next treatment and EFS will also be analyzed using Kaplan-Meier methods. The same type of presentations as for TTP and PFS will be prepared.

In addition, time to first response, time to best response and time to first clinical benefit will be analyzed using Kaplan-Meier methods restricted to the subgroups of responders without having any censored subjects. The same type of presentations as for TTP and PFS will be prepared.

Duration of response and further duration variables defined in section 7.3.3.3 will also be analyzed using Kaplan-Meier estimates for median, 25% and 75% quantile, but this analysis will be restricted to the subgroup of subjects with response or in general, the subgroup of subjects where the duration can be calculated

Kaplan-Meier plots for all time-to-event variables will be provided for combined data.

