4.2 Final Analysis

The analyses identified in the protocol and in this SAP will be performed after all subjects enrolled have reached the Cycle 3 Day 1 visit or end of study assessments (whichever comes first) and all relevant study data have been processed, all relevant data has been frozen and this SAP has been approved. A cut-off date will be determined for the analysis (which will be after all subjects enrolled have reached Cycle 3 Day 1 or end of study assessments) and all data available up to the cut-off date will be included into the analysis. The final analysis is also referred to as “primary completion analysis”.

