Categorical, qualitative variable summaries will include the frequency and percentage of subjects who are in a particular category. Unless otherwise stated the calculation of proportions will be based on the number of subjects of the analysis set of interest. Therefore counts of missing observations will be included in the denominator and presented as a separate category. [REDACTED]

The last pre administration observation will be used as the baseline value for calculating post administration changes from baseline. Thus baseline will be Cycle 1 Day 1 in case there is a value available (not missing) and screening otherwise.

All data obtained on the electronic case report for (eCRF) and entered into the database will be provided in separate data listings showing individual subject values. The planning and reporting of statistical analyses will be carried out as described in the Premier Research Biostatistics standard operating procedures.

Any subject who withdraws from the study will be analyzed with the data available. Imputation of missing values will not be performed.

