7.3.3 Efficacy Endpoints Based on Investigator Assessment

The Investigator will assess efficacy at specific study visits according to the response criteria for MM as defined in section 18.3 of the study protocol version valid at the time of the assessment. All of the criteria are based on the International Myeloma Working Group (IMWG) Uniform Response Criteria [6], except for MR, which is based on the (adopted) European Group for Blood and Marrow Transplantation (EBMT) criteria [7].

The response evaluation of the Investigator is based on the serum and urine M-protein levels, and, where applicable, the serum FLC level, and FLC ratio.

The categories of overall tumor response assessment of the Investigator will be as follows:

- sCR – Stringent Complete Response
- CR - Complete Response
- VGPR - Very Good Partial Response
- PR - Partial Response
- MR - Minimal Response
- SD - Stable Disease
- PD - Progressive disease
- Missing (if response assessment is not done)

In case of progressive disease, the date of progression will be given by the Investigator.

All responses need 2 consecutive assessments, ideally being confirmed at Day 1 of the next cycle. Thus all endpoints defined to evaluate responses per-subject across time points (see section 7.3.3.2 and 7.3.3.3) will include confirmed responses only.

For all endpoints where dates are used in the derivations (e.g. date of first response, date of first

progression), the following dates will be taken into consideration to determine the time point each response assessment refers to:

- Date of assessment or date of visit, whichever is earlier if the assessment is non-PD (this approach is chosen as the assessment is sometimes done retrospectively and not at the date of the visit)
- date of progression given by the Investigator in the field “Date of Progression” in the response assessment form if the assessment is PD

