7.3.3.1 Responses by subject and visit

The following variables will be derived by visit based on the overall tumor assessment of the Investigator:

Any response (PR or better) (yes/no) by visit:

- yes, if tumor response assessment is sCR, CR, VGPR, or PR
- no, if tumor response assessment is MR, SD, PD or Missing

Any clinical benefit (MR or better) (yes/no) by visit:

- yes, if tumor response assessment is sCR, CR, VGPR, PR or MR
- no, if tumor response assessment is SD, PD or Missing

Any disease control (SD or better) (yes/no) by visit:

- yes, if tumor response assessment is sCR, CR, VGPR, PR, MR or SD
- no, if tumor response assessment is PD or Missing

7.3.3.2 Responses derived per-subject across time points:

The subsequent variables will be derived per-subject across time points, based on the overall tumor assessment of the Investigator.

Best Overall Response (BOR): The best overall response will be defined as the best response across all time points. The best possible overall response is sCR, followed by CR, VGPR, PR, MR, SD, and PD.

To be assigned a status of sCR, CR, VGPR, PR, MR, SD, the first assessment must be confirmed by the next consecutive non-missing assessment (missing values will not be taken into account). Both assessments must show a status of sCR, CR, VGPR, PR, MR or SD, and the assigned confirmed status will be the weaker status of both assessments.

A single progression of disease (PD) assessment which did not cause a discontinuation of

treatment and which has been disproven by the next consecutive non-missing tumor assessment will not be considered in the evaluation of best overall response. If no post-baseline confirmed response assessment or PD is available, then the best overall response will be “Not Evaluable” (NE).

Secondary efficacy endpoint variables:

Any response (yes/no) in study:

- yes, if best overall response is sCR, CR, VGPR or PR
- no, if best overall response is MR, SD, PD or NE

The **Overall response rate (ORR)**, defined as the proportion of subjects who meet the criteria of confirmed sCR, CR, PR or VGPR at any time during study, will be calculated from this variable.

Additional efficacy variables:

Any clinical benefit (yes/no) in study:

- yes, if best overall response is sCR, CR, VGPR, PR or MR
- no, if best overall response is SD, PD or NE

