8. STUDY SUBJECTS AND DEMOGRAPHICS

8.1 Disposition of Subjects and Withdrawals

All subjects who provide informed consent will be included in the database and will thus be accounted for in this study. Descriptive summaries of population data will be presented for the total population and the safety population and will include

- The frequency and percent of subjects in each study population
- The disposition of subjects including
 - number of subjects screened, who failed screening and who are eligible
 - number of subjects treated
 - number of subjects who completed 1st treatment cycle (subjects with number of cycles completed ≥ 1 , see definition in section 7.3.6)
 - number of subjects who completed of 2nd treatment cycle (subjects with number of cycles completed ≥ 2 , see definition in section 7.3.6)
 - number of subjects with at least one Cycle 3+ treatment
 - number of subjects who terminated the study
 - number of subjects still ongoing
- Study discontinuations for all subjects treated by reason (as specified in eCRF) (safety population only)
- time on study [months] and duration of treatment [months] (see definition in section 7.3.6)

Moreover, a listing of screening failures with corresponding reasons will be provided.

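### At the primary completion analysis, subjects whose C6D1 or C12D1 falls after the cut-off count as non-responders, which lowers these two by-visit ORR, CBR and DCR columns in late-enrolling groups

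*SAP*

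**What the plan says.** - **Timing.** Under SAP 4.2 the analyses "will be performed after all subjects enrolled have reached the Cycle 3 Day 1 visit or end of study assessments", whichever comes first. The cut-off date is chosen later, at or after that point, and data up to it are used. Nothing requires C6D1 or C12D1 to have been reached.
- **Visits tabulated.** SAP 9.2 gives each response category, and ORR, CBR and DCR, "by visit (for C3D1, C6D1, and C12D1").
- **Coding.** SAP 7.3.3 defines the last response category as "Missing (if response assessment is not done"). SAP 7.3.3.1 then sets by-visit response to "no, if tumor response assessment is MR, SD, PD or Missing". Clinical benefit and disease control treat Missing the same way.
- **Denominator.** SAP 9.2: "The denominator for calculating the rates (rates by visit and best response rates) will be the total number of subjects" in the analysis group. This follows protocol 15.4. SAP 7.1 adds that "counts of missing observations will be included in the denominator and presented as a separate category".
- **Explicit missing-data rule.** The sentence on missing visits in SAP 9.2 covers withdrawals and protocol non-compliance after new anti-myeloma therapy. The available text has no rule for a subject still on study whose visit is not yet due.
- **Later analysis.** SAP 4.3 plans to repeat all analyses with longer follow-up.

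**The concern.** Counting subjects who progressed, died or withdrew as non-responders at a later visit is a deliberate and reasonable choice. A subject who has simply not been on study long enough is different: the outcome at that visit is unknown because of the calendar, not because of the disease or the treatment. The rules above treat the two alike.

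The shortfall depends on enrolment date. Part A levels 1 to 7 are tested in sequence, and cohorts 7d and 7e may open only after 7c is complete. The Part D and E confirmation cohorts follow escalation in those parts, so they are the likeliest to be touched. A late group could look worse than an early one at C6D1 and C12D1 purely because it enrolled later. On the categories listed in SAP 9.2, missing is the only row available for these subjects, so they would sit with those who withdrew or were not assessed.

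**Working it through.** The documents state no figure for by-visit response rates, so there is none to reproduce. The check uses the visit calendar and the coding rules.

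**Inputs from the documents**
- 28-day cycles (SAP 3.1).
- Study duration about 8 years (protocol 7.2); follow-up at most 3 years per subject (protocol 7.1).
- Recommended-dose group of at least 9 subjects, 6 of them from the confirmation cohort (SAP 5).

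**Assumed, because the documents do not give them**
- Accrual length of the group: 12 to 60 months. The upper end is 8 − 3 = 5 years for the whole trial; 12 months is an assumed lower end for one part.
- Uniform accrual, the earliest permitted cut-off, and a true rate of 40% at each visit.

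**Step 1: visit gaps.** Days from Cycle 1 Day 1 = (cycle − 1) × 28: C3D1 56, C6D1 140, C12D1 308. Gaps from C3D1 are 140 − 56 = 84 days and 308 − 56 = 252 days. At 30.44 days per month these are 2.76 and 8.28 months. At the earliest cut-off, only groups still enrolling within about 84 days (C6D1) or 252 days (C12D1) of the start of the subject whose C3D1 sets the cut-off are affected.

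**Step 2: effect on the rate.** With f the share of the group whose visit date falls after the cut-off, reported rate = true rate × (1 − f). Under uniform accrual f = gap ÷ accrual length.

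| Accrual (months) | f at C6D1 | Reported C6D1 | f at C12D1 | Reported C12D1 |
|---|---|---|---|---|
| 12 | 2.76/12 = 0.230 | 30.8% | 8.28/12 = 0.690 | 12.4% |
| 24 | 0.115 | 35.4% | 0.345 | 26.2% |
| 36 | 0.077 | 36.9% | 0.230 | 30.8% |
| 60 | 0.046 | 38.2% | 0.138 | 34.5% |

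**Step 3: smallest recommended-dose group.** With n = 9 and k subjects whose visit is after the cut-off, the rate cannot exceed (9 − k)/9. For k = 1 that is 88.9%, and a true 40% shows as 35.6%. For k = 3 the cap is 66.7%, and 40% shows as 26.7%.

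**Step 4: what is untouched by this rule.** C3D1, because every subject has reached it or ended the study; groups closed early enough before the cut-off; the rates based on best overall response, which carry the exact intervals; and the Kaplan-Meier endpoints.

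**The case against.** The strongest reply has four parts.

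1. **The text is incomplete.** Words after the SAP 7.1 missing-data rule and the table descriptions are redacted, and the reporting conventions listed as section 11 are not in the available text. A convention for visits not yet due may exist there. This stands as a caution about the row layout. It does not change the rate: even if such a visit were never labelled Missing, the fixed denominator in SAP 9.2 gives the same figure.
2. **The denominator is the protocol's own.** This is true, and it is why the proposal keeps the planned rate and adds a second one beside it.
3. **The effect may be nil, and the low figures stack assumptions.** This also stands. SAP 4.2 fixes only the earliest cut-off. The 12.4% needs short, late accrual, the earliest cut-off and a true rate still at 40% some ten months in. Recommended-dose tables pool escalation and confirmation subjects, which lengthens the accrual span and reduces f.
4. **Little depends on these columns, and a reader has other sources.** The study is not randomised, and no interval, test or decision uses the columns. Individual data "will be provided in separate data listings showing individual subject values", SAP 8.1 reports the "number of subjects still ongoing", and SAP 4.3 repeats everything. These points limit the harm to the first report, but they leave its tabulated rates lowered.

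**Conclusion.** The concern holds and is minor. Read together, SAP 4.2, 7.3.3.1 and 9.2 multiply the C6D1 and C12D1 rates in late-enrolling groups by (1 − f) at the primary completion analysis. Confidence in the mechanism is high; its size cannot be fixed from the documents. Under the stated assumptions a true 40% shows as 30.8% to 38.2% at C6D1 and 12.4% to 34.5% at C12D1. A later cut-off reduces the loss, possibly to zero, and a true C12D1 rate below 40% makes it smaller in percentage points. Where f differs between groups, these two columns should not be compared across early and late dose levels in the first report.

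**What to change.** In SAP 9.2, for C6D1 and C12D1 at the primary completion analysis:

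- Keep the planned rate and add, beside it, a rate limited to subjects whose Cycle 1 Day 1 is early enough before the cut-off for the visit to have occurred: nominal day, plus the 2-day visit window, plus a fixed allowance for cycle delays stated in the SAP before the cut-off is chosen.
- Apply the date rule to all subjects alike, and keep eligible subjects who progressed, died or withdrew as non-responders, so that selection does not depend on outcome.
- Show visits not yet reached in a row separate from missing.

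The allowance is needed because dosing may be delayed by up to 14 days (protocol 8.6) and Day 1 of the next cycle then moves. The latter rule is in protocol 9.1.4, which concerns POM, LEN and DEX; extending it to monotherapy is an inference. As an upper illustration, one 14-day delay at each cycle start adds 5 × 14 = 70 days before C6D1 and 11 × 14 = 154 days before C12D1. The required lead is then 140 + 2 + 70 = 212 days and 308 + 2 + 154 = 464 days.

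The cost is a few lines of SAP text, one derived date flag, one extra rate and one table row. The drawback is smaller denominators at the later visits, more so with a generous allowance. There is no departure from protocol 15.4 while the planned rate stays; replacing it would have to be recorded under protocol 15.13. Deferring both visits to the SAP 4.3 analysis takes only one sentence, but is the weaker choice because it drops usable columns for the early cohorts.

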9.2.1 Subgroup Analysis

For BOR, ORR, CBR, DCR and PFS, subgroup analyses will be performed within the subgroups defined in section 7.4. The data will be presented in the same format as described above, within those subgroups of the safety population. The subgroup analysis will only be performed for combined presentations.

9.3 Pharmacodynamic Analysis

All pharmacodynamic analyses, except of serum and urine M-protein, and serum FLCs, will be performed for the safety population only.

MorphoSys AG will perform further post hoc exploratory analysis to investigate correlations between different biomarkers and response variables, which are not further described in this SAP.

In general, pharmacodynamic analyses by visit will only include all cycles until Cycle 6, Cycle 12 and EOS.

9.3.1 Pharmacodynamic Parameters Measured in Blood or Urine

Actual values and absolute and percent changes from baseline will be summarised descriptively by visit for the pharmacodynamic parameters specified below. Moreover, 95%-confidence intervals will be provided for mean and median changes in summaries of absolute changes from baseline and for median changes in summaries of percentage changes from baseline in all combined presentations.

Measurements of B, T, and NK cell populations and CD16 expression on NK cells: Descriptive summaries (as specified above) will be provided for the following parameters:

- Measurements of B, T, and NK cells [%]
Measurements of B, T, and NK cells [/ μ l]

Measurements of B, T, NK cells are given in % and/or as absolute count [/ μ l] by the investigator, whereas the absolute count is often missing. Therefore absolute count [/ μ l] will be also be derived using the lymphocytes absolute values [G/l = $n \cdot 1000 / \mu$ l = /nl] from the laboratory hematology data (lymphocytes absolute * [measurement in % /100]

* 1000, rounded without decimals). Two tables each will be presented, one table based on % values (original values only) and a further table based on absolute counts [μl] (derived and original values, both rounded without decimals).

- CD16 expression on NK cells [Antibodies bound per cell]

The analysis will be based on the unit “antibodies bound per cell”. Measurements cannot be included in the analysis if measurements in the unit “antibodies bound per cell” are missing.

Result of Flow Cytometry of Peripheral MM Cells: Descriptive summaries will be provided for the following parameters:

- Measurements of CD138 cells [Count per 10^6 cells]
- Percentage of malignant CD38 cells [%]
- Measurement of CD38 expression on malignant cells in [MFI] (MFI = Median Fluorescence Intensity)
- Measurement of CD38 expression on malignant cells in [Antibodies bound per cell]

In the summaries of actual values for CD38 variables, only subjects who have counts of CD138+ cells equal and above 100 counts per 10^6 cells at the corresponding visit will be included since for subjects who have counts of CD138+ cells below 100 counts per 10^6 cells no values for CD38 variables will be available. In the summary of absolute and percentage changes from baseline for CD38 variables, only subjects who have counts of CD138+ cells above 100 counts per 10^6 cells at both baseline and post-baseline visits will be included.

Serum and Urine M-Protein, Serum FLCs: Serum and urine M-protein and serum FLCs were analyzed by a local laboratory at the beginning of the study and by central laboratory enrolled after November 2014 (starting from cohort 7c/ cohort 8 partially, see section 7.3.4 for parameters measured and derived). Descriptive summaries by visit (including summaries of absolute and percentage changes) will be provided for the following parameters by visit:

- Serum M-protein level [g/L]
- Urine M-protein result [g/24h]
- Lambda FLCs [mg/L]
- Kappa FLCs [mg/L]
- Kappa/lambda FLC ratio

Moreover, descriptive summaries across time points will be prepared for

- relative change (%) in serum M-protein result from baseline to post-baseline nadir
- relative change (%) in urine M-protein result from baseline to post-baseline nadir.

Anti-TT data (Anti-Tetanus Toxoid IgG data): Anti-TT data will only be presented in listings.

9.3.2 Pharmacodynamic Parameters Measured in Bone Marrow

A bone marrow examination will be performed at screening (results from bone marrow examination done within 4 weeks prior to screening are also acceptable, if the subject has been hematologically stable since then). Post-baseline bone marrow data will only be assessed for

subjects who provided an additional informed consent at follow-up visit, or at the Cycle 2 Day 1 visit for subjects enrolled after Nov 2014 (starting from cohort 7c/ cohort 8 partially). Descriptive summaries will be provided for baseline and post-baseline values of the parameters specified below. Summaries for absolute and percentage changes are not planned to be provided, because of the expected low number of subjects who have bone marrow data after start of treatment. However, these may be added if a sufficient number of subjects with post-baseline bone marrow data will be available.

Bone Marrow Histology: Descriptive summaries of actual values will be provided for the following parameters:

- % of plasma cells
- Myeloid to erythroid ratio
 - The myeloid to erythroid ratio will be given in the format “xx:xx”. For descriptive summary tables the quotient will be calculated.

All other parameters (Cellularity, histology of plasma cells, histology of erythroid cells, histology of myeloid cells and histology of megacaryocytes) will only be included in listings since these are captured as free text.

Immunophenotyping of MM cells (bone marrow): Descriptive summaries of actual values will be provided for the following parameters:

- Measurements of CD138 cells [% of all bone marrow cells]
- Measurements of CD38 cells
 - Percentage of malignant CD38 cells [%]
 - Measurement of CD38 expression on malignant cells in [HIT2 MFI]
 - Measurement of CD38 expression on malignant cells in [QuantiBrite™ MFI]
 - Measurement of CD38 expression on malignant cells in [HIT2 Antibodies bound per cell]
 - Measurement of CD38 expression on malignant cells in [QuantiBrite™ Antibodies bound per cell]

